9.7 Study Follow Up

Study-related follow-up visits occur at the investigational site at, 72 Hours (Visit 4) Post-TKA as well as Week 2 (Visit 5), Week 6 (Visit 6), and Week 12 (Visit 7) Post-TKA. The study's schedule of assessments is shown in Table 2.

Follow Up Visit 4 (72 hours \pm 24 hours post op) - Phone Call

Visit 4 (72 Hours Post-TKA) will occur via a phone follow-up. No physical performance measures will be collected at these visits. Subjects will self-report the amount of opioids used. Subjects will report the NRS Pain Scores, answer the KOOS Jr. questions and report any AEs if present.

[figure not shown]
Follow Up Visit 5 (2 Weeks; \pm 3 Days Post Op), and Visit 6 / 6 Weeks Post-op (6 weeks; \pm 5 Days Post-Op)

Subjects will be evaluated and data collected per the schedule of events. Any changes in concomitant medications/concurrent procedures will be documented. Any anticipated observations, adverse events, adverse device effects and/or SAE/UADE/USADE will be assessed and documented. Photographs may be taken of the treatment area.

The Subject will complete a KOOS JR. questionnaire and NRS for Pain when standing from a seated position for all follow-up visits. The Subject will also complete a [REDACTED] [REDACTED] will answer Satisfaction questions at Visit 6.

The subject will complete the Physical Performance Measures for Visit 5, 6 and 7 in the following order under supervision of the investigator or designee:

- ! [REDACTED]
- Time Get-Up and Go

Subjects will be asked to bring all prescription opioid bottles to all study follow-up visits. A pill count will be completed by the study coordinator, or designee, and opioid medication will be returned to subjects.

Follow Up Visit 7 (12 Weeks; \pm 7 days Post-Op)

Subjects will be evaluated and data collected per the schedule of events. Any changes in concomitant medications/concurrent procedures will be documented. Any anticipated

observations, adverse events, adverse device effects and/or SAE/UADE/USADE will be assessed and documented. Photographs may be taken of the treatment area.

The Subject will complete a KOOS Jr. questionnaire, NRS for Pain when standing from a seated position. The Subject will also complete a [REDACTED] will answer Satisfaction questions.

The subject will complete the Physical Performance Measures in the following order under supervision of the investigator or designee:

- Get up and Go Test

The total number of outpatient Physical Therapy visits conducted between each study visit will also be obtained. Additional Data collected from Physical Therapy Visits will include:

- Pain while seated

Subjects will be asked to bring all prescription opioid bottles to all study follow-up visits. A pill count will be completed by the study coordinator, or designee, and opioid medication will be redisensed to subjects.

At the completion of this visit, the Subject will be exited from the study unless the Subject has any ongoing device-related or iovera^o treatment-related adverse events as described in section 10.8.

Table 2. Schedule of Assessments

Assessment	Visit 1 / Screening	Visit 2 / Iovera [®] Treatment	Visit 3 / DAY OF TKA (Day 0)	Visit 4 / 72 Hours Post-op	Visit 5 / 2 Weeks Post-op	Visit 6 / 6 Weeks Post-op	Visit 7 / 12 Weeks Post-op
Informed Consent	X						
Eligibility	X	X					
Medical history	X	X					
Concomitant medication assessment	X	X	X	X	X	X	X
Prior/Concurrent Therapy	X	X		X	X	X	X
Randomization*	X						
Study Treatment		X					
Physical Exam	X						
Vital signs	X	X					
Knee Circumference	X						
KOOS JR. Questionnaire	X			X	X	X	X
NRS for Pain	X			X	X	X	X
Subject Satisfaction Questions						X	X
Physical Performance Measures	X				X	X	X
Pain Medication Accountability				X	X	X	X
AE/SAE Assessment		X	X	X	X	X	X

* Randomization occurs after the subject has met eligibility criteria

Follow-up visits generally consist of the following:

- The Investigator or designee assesses the occurrence of health status changes and adverse events since last study visit;
- The Investigator or designee determines whether any changes in daily medications have occurred;
- The Investigator or designee performs drug accountability (pill counts) of post-operative outpatient opioid medication and re-dispenses unused opioid medications to subjects after use. The Investigator or designee records other over-the-counter concurrent pain medication use and pain relief therapies used per subject report;
- The Subject completes a KOOS JR. questionnaire, [REDACTED] Satisfaction questions (Visit 6 and 7 only), and reports NRS for Pain when standing from a seated position;
- The Investigator or designee performs Physical Performance Measures ([REDACTED] Get Up and Go Test).

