9.9 Study Exit

When the final study visit is complete, the Subject's participation in the study is complete and the Investigator, or designee, will complete the study exit CRF.

If a Subject is experiencing an unresolved device or iovera[°] treatment related adverse events at the final study visit, the Subject will be followed by the Investigator until resolution occurs.

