10.4 Study Endpoints

10.4.1 Primary Effectiveness Endpoint

The primary effectiveness endpoint is the cumulative consumption of opioids from the time of hospital discharge to 6 weeks post-TKA Surgery. Opioid consumption will be converted to morphine equivalents, and subject consumption will be verified by pill count at follow-up visits. The cumulative morphine equivalent will be divided by the number of days to provide the Total Daily Morphine Equivalent (TME) for the subject.

The difference in the mean TME between the two treatment groups will be calculated as Standard of Care TME mean – Active TME mean, such that a positive difference indicates that the Standard of Care Treatment group had a larger mean TME than the Active Treatment group, while a negative difference indicates the opposite. A positive difference between the two treatment groups reflects a positive outcome for the study.

Let $\mu_{1,Active}$ and $\mu_{1,SOC}$ denote the true mean TMEs for the active and standard of care treatments, respectively. Then the null and alternative hypotheses for the primary effectiveness endpoint are as follows:

$$H_0: \mu_{1,Active} \geq \mu_{1,SOC}$$

$$H_1: \mu_{1,Active} < \mu_{1,SOC}$$

A one-sided, two-independent sample, Satterthwaite t-test will be used to test the null hypothesis. The Primary Effectiveness Study Objective will be met if this t-test is statistically significant using a one-sided $\alpha = 0.025$ level of statistical significance.

This endpoint will be summarized by treatment group using descriptive statistics. The difference in mean TMEs between the two treatment groups and a 95% confidence interval based on the t-distribution for the true difference in the mean TMEs between the two treatments will also be provided.

The database will be “soft-locked” after all 6 week data has been collected (all data monitored with the exception of data points collected beyond 6 weeks). An interim analysis of the primary endpoints will be performed on the soft-locked data for internal Myoscience purposes. The full dataset will be locked upon completion of all visit and adverse event follow-ups and this data will be reported in the clinical study report.

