10.8 Sample Size Determination

The required sample size was determined based on providing at least 80% power for the primary effectiveness endpoint using a one-sided, two-independent sample, Satterthwaite t-test to test for non-inferiority of iovera treatment to Standard of Care treatment, with a significance level of 0.025, assuming a 1:1 allocation to treatment, a true treatment effect ($\mu_{1,Active} - \mu_{1,SOC}$) of -12.0 mg, and true standard deviations of 16.9 mg and 26.0 mg, for the iovera and Standard of Care treatments, respectively. Based on these specifications, the required sample size is 57 subjects per treatment group, for a total of 114 subjects. To account for a small number of the subjects withdrawing early or not having data available for the analysis of the primary effectiveness endpoint, the required sample size was increased to 120 randomized subjects (approximately 60 Active Treatment subjects and 60 Standard of Care Treatment subjects).

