11. ADVERSE EVENTS

The study Investigator and Coordinator will evaluate, characterize and record in the CRF all adverse events (AEs) occurring in all subjects from the initiation of study treatment to study exit (or premature withdrawal). Device or procedure related AEs will be followed until resolution. AEs may be reported spontaneously by the subject or detected by the Investigator or coordinator. AEs should be evaluated for diagnoses not just symptoms (i.e., “angina”, not “chest pain”).

AEs may be either spontaneously reported or elicited during questioning and examination of a subject. All AEs must be completely recorded within the Subject's source documentation. All AEs will be evaluated by the Investigator for relationship to the iovera[°] device and to the treatment.

In addition to verbatim terms, the Sponsor will categorize all AEs using MedDRA preferred terms and system organ classes (SOC). Analysis will report both verbatim and MedDRA terms.

Adverse events¹ (AEs) will be assessed continuously from the initiation of study treatment through study exit. Per ISO14155:2011, an AE is any untoward medical occurrence, unintended disease or injury, or untoward clinical signs in subjects, users or other persons, whether or not related to the investigational medical device. An AE can arise from any use of the device (e.g., off-label use, use in combination with any drug) and from any route of administration.

Timely and complete reporting of all AEs assists the Sponsor in identifying any untoward medical occurrence, thereby allowing:

- 1) protection of the safety of study subjects;
- 2) a greater understanding of the overall safety profile of the device;
- 3) recognition of device-related ill effects;
- 4) appropriate modification of study protocols;
- 5) improvements in study design or procedures; and
- 6) adherence to worldwide regulatory requirements.

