### **5.4 Interim Analysis**

The analyses addressed in this SAP will utilize the final, locked database.

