	Minimally worse	n (%)	xx (xx.x)	xx (xx.x)
	No change	n (%)	xx (xx.x)	xx (xx.x)
	Minimally improved	n (%)	xx (xx.x)	xx (xx.x)
	Much improved	n (%)	xx (xx.x)	xx (xx.x)
	Very much improved	n (%)	xx (xx.x)	xx (xx.x)
	Overall knee pain status since the beginning of the study (1)	n Mean Median SD Minimum - Maximum	xx x.x x.x x.x x - x	xx x.x x.x x.x x - x
	Subject satisfaction with pain management following surgery (2)	n Mean Median SD Minimum - Maximum	xx x.x x.x x.x x - x	xx x.x x.x x.x x - x
Week 12	...	...	...	...

[figure not shown]
Program Name:

Creation date, time

(1) Very much worse=-3, Much worse=-2, Minimally worse=-1, No change=0, Minimally improved=1, Much improved=2, Very much improved=3.

(2) Measured on a scale of 0 to 10, with 0 being very unsatisfied and 10 being very satisfied.

[figure not shown]

Table 15

STUDY EXIT  
ITT POPULATION

Variable	Iovera (N=xx) n (%)	Standard of Care (N=xx) n (%)
Primary Reason Off Study		
Completed all visits	xx (xx.x)	xx (xx.x)
AE/SAE	xx (xx.x)	xx (xx.x)
Lost to follow-up	xx (xx.x)	xx (xx.x)
Non-compliant participant	xx (xx.x)	xx (xx.x)
Withdrew consent	xx (xx.x)	xx (xx.x)
Death	xx (xx.x)	xx (xx.x)
Investigator decision	xx (xx.x)	xx (xx.x)
Medical need for prohibited medications or treatment	xx (xx.x)	xx (xx.x)
Other	xx (xx.x)	xx (xx.x)
Did subject exit with unresolved adverse events?		
Yes	xx (xx.x)	xx (xx.x)
No	xx (xx.x)	xx (xx.x)

Program Name:  
Source: Listing 1

Creation date, time

Table 16

PROTOCOL DEVIATIONS  
ITT POPULATION

Type of Protocol Deviation	Iovera (N=xx) n (%)	Standard of Care (N=xx) n (%)
Any Protocol Deviation	xx (xx.x)	xx (xx.x)
Subject consent not obtained prior to study procedures	xx (xx.x)	xx (xx.x)
Eligibility criteria not met	xx (xx.x)	xx (xx.x)
Pre-treatment assessment not complete	xx (xx.x)	xx (xx.x)
Iovera Treatment not complete	xx (xx.x)	xx (xx.x)
TKA surgery deviation	xx (xx.x)	xx (xx.x)
Anesthesia/analgesia deviation	xx (xx.x)	xx (xx.x)
Post-treatment/follow-up assessment not complete	xx (xx.x)	xx (xx.x)
Follow-up out of window	xx (xx.x)	xx (xx.x)
Follow-up visit not done	xx (xx.x)	xx (xx.x)
Other: Incorrect Prescription (1)		
Other: reason	xx (xx.x)	xx (xx.x)

Program Name:

Creation date, time

Source: Listing 3

Note: A subject can have more than one type of protocol deviation, so the percentages may sum to more than 100%.

(1) Includes deviations due to patients not taking Tramadol.

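### Protocol 9.7 and 9.9 give different exit rules for a subject with an ongoing device- or iovera-related AE, so the AE recording period and the Table 15 exit status can depend on treatment arm

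*Protocol*

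**What the plan says.** Protocol section 9.7, on Visit 7 (Week 12), states that "the Subject will be exited from the study unless the Subject has any ongoing device-related" events; the sentence continues to "treatment-related adverse events as described in section 10.8". The section it refers to is "10.8 Sample Size Determination", which contains no AE or exit rule.

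Protocol section 9.9 says that once the final study visit is complete, the subject's "participation in the study is complete and the Investigator, or designee, will complete the study exit CRF". Its second paragraph adds that a subject with an unresolved device- or treatment-related AE at that visit is followed by the investigator until it resolves. Section 11 also requires follow-up of related AEs to resolution, and sets the recording period for all AEs as "from the initiation of study treatment to study exit (or premature withdrawal").

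SAP section 10.0 summarises AE status at study exit by arm. The Table 15 row is "Did subject exit with unresolved adverse events", answered Yes or No for AEs of any cause.

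On the lock, protocol 10.4.1 says "The full dataset will be locked upon completion of all visit and adverse event follow-ups", and 10.4.2 repeats this. SAP 5.4 says "The analyses addressed in this SAP will utilize the final, locked database".

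**The concern.** Study exit does two jobs in the safety analysis: it closes AE recording and it fixes the date at which unresolved AEs are counted. If exit is put off for some subjects, both dates move for them. Under 9.7 the trigger is an event that only a subject who received iovera can have, so the dates can move in one arm and not in the other.

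Two summaries are exposed. The treatment-emergent AE (TEAE) tables in SAP 9.0 report subject counts and percentages, plus event counts, with no adjustment for length of observation. Table 15 is the only summary in the visible table shells that compares unresolved AEs between arms. How long side effects last is a natural safety question for a device that lesions sensory nerves, so the two columns should refer to the same time point.

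**Working it through.** The plan states no figure to reproduce. The check is a comparison of the text, with simple arithmetic on assumed values.

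**1. The two exit rules.** Take a subject at Visit 7 with an ongoing related AE.
- Section 9.7: not exited. No later exit date is given, and the cross-reference does not supply one.
- Section 9.9, first paragraph: participation complete and exit form filled in, with no exception. Second paragraph: the AE is then followed to resolution.

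**2. Who can meet the 9.7 exception.** The AE must be related to the device or to the iovera treatment. A control subject who did not receive iovera cannot have one. A control with an unresolved surgical or opioid AE exits at Week 12 under both sections.

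**3. AE recording period.** Inputs from the protocol: treatment 5 days before surgery (section 9.5, ± 2 days) and Week 12 = 84 days after surgery. Base period = 5 + 84 = 89 days. The share of the arm affected (f) and the extra days before exit (x) are not in the documents and are assumed: f from 2% to 20%, x from 28 to 90 days. The mean increase in the iovera arm is f × x:
- low: 0.02 × 28 = 0.56 days; 0.56 / 89 = 0.6%
- middle: 0.05 × 56 = 2.8 days; 2.8 / 89 = 3.1%
- high: 0.20 × 90 = 18 days; 18 / 89 = 20%

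With exit at Visit 7, as in 9.9, the increase is 0.

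**4. Table 15.** With about 60 iovera subjects, the same assumed f gives 60 × 0.02 = 1.2 to 60 × 0.20 = 12 subjects whose answer could change from Yes (status at Visit 7) to No (status at a deferred exit). This is an upper limit for each f: it requires that the AE resolves before exit and that the subject has no other unresolved AE.

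**5. Is the situation foreseeable?** Section 8.4 lists altered sensation as a known risk. Section 1 gives a duration of effect of two to three months, and Week 12 falls about 89 days after treatment. Some related AEs could be ongoing then; the documents do not say how many.

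**6. Participation limit.** Section 5 allows up to 16 weeks = 112 days. Screening at Day -30 to Week 12 is already 30 + 84 = 114 days, or 121 with the +7-day window. For a subject screened that early, the limit leaves no room for a deferred exit.

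**7. Lock.** Sections 9.9 and 11 require follow-up to resolution whether or not the subject has exited, and 10.4.1 and 10.4.2 tie the lock to completed AE follow-up. The wait is therefore the same under either exit rule. No end is stated for a related AE that does not resolve.

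**The case against.** The strongest reply is that this is an editing slip. The stale reference to section 10.8 suggests as much, and the stated maximum participation fits exit at Week 12. No visit is scheduled after Visit 7, so any longer recording period is nominal, with no planned contact at which new AEs would be sought. Listing 2.2 gives AE status at each visit including Week 12, the outcome and the resolution date, and Listing 2.1 gives relatedness, so the information is kept under either rule. All of this stands, and it keeps the point small. It does not tell a site when to complete the exit form or stop recording new AEs, and a by-subject listing is not an arm comparison.

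One could also read the second paragraph of 9.9 as an exception to the first, so that both sections defer exit. The text does not say so, and on that reading the arm-dependent dates would follow from both sections.

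A reader might infer several stronger claims that the documents do not support:
- *Table 15 must show no unresolved device effects in the iovera arm.* Subjects who leave early under section 9.10 can still exit with one, and the row pools AEs of every cause.
- *The 9.7 rule is what delays the final lock.* The lock wait is the same under 9.9.
- *AE recording in the iovera arm is extended without limit.* Section 9.7 sets no such rule, and the need for resolution comes from 9.9 and 11. The extension concerns only subjects with an ongoing related AE at Visit 7.

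**Conclusion.** The two sections conflict, and the reference that should settle the matter points to the wrong place. If 9.7 is followed, the iovera arm can have a longer nominal AE recording period, and related AEs ongoing at Week 12 can drop out of its Yes count in Table 15 once resolved, while control subjects who complete the study are classified at Week 12.

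This is a minor point, limited to safety reporting for subjects who reach Visit 7 with an ongoing related AE. Its size cannot be derived from the documents; the 0.6 to 18 days and the 1 to 12 subjects rest wholly on the assumed shares and durations. The 6-week primary and secondary endpoint values are unaffected. The open-ended wait for the lock is a separate matter that exists under either exit rule, so reconciling the exit rules alone would not remove it.

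**What to change.** 1. Reconcile protocol 9.7 with 9.9 and 11, and correct the section 10.8 reference.
2. In both arms, complete the exit form and record unresolved-AE status as of Visit 7, or as of withdrawal if earlier.
3. Use that same date as the AE cut-off for all TEAE tables and for Table 15. This takes one sentence each in SAP 9.0 and 10.0 and a footnote to Table 15.
4. Leave the existing follow-up of related AEs to resolution unchanged, and report it in Listing 2.2.
5. Amend the lock sentences in protocol 10.4.1 and 10.4.2 so that the lock refers to this data cut.

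The cost is a few sentences and a footnote, with no added visits or assessments. The small downside is that AEs arising after the cut-off appear in listings only, not in the summary tables.

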9.8 Photographs

Photographs are optional; and may be requested by sponsor in the event a local skin reaction occurs at the treatment site. Photographs will be labeled appropriately, stored electronically (e.g., JPEG, PNG or other relevant format) and sent to the Sponsor according to Sponsor instructions.

9.9 Study Exit

When the final study visit is complete, the Subject's participation in the study is complete and the Investigator, or designee, will complete the study exit CRF.

If a Subject is experiencing an unresolved device or iovera[°] treatment related adverse events at the final study visit, the Subject will be followed by the Investigator until resolution occurs.

9.10 Subject Discontinuation

A Subject may be withdrawn from the study prior to completion for any of the following reasons:

- Voluntary withdrawal of consent
- Adverse event preventing continued study participation
- Investigator believes risk of further subject participation outweighs benefit
- Medical need for prohibited medications or treatment
- Persistent non-compliance or lost to follow-up (A Subject is considered lost to follow-up after the site makes 3 attempts to contact the Subject via email or phone call and a certified letter is sent to the Subject.)

The Investigator/Coordinator will complete a study exit form in the CRF for any subject who prematurely discontinues from the study. If discontinuation was the result of an AE, the AE will also be recorded in the CRF.

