9.4 Randomization

After meeting all of the inclusion and none of the exclusion criteria and prior to study treatment, Subjects will be randomized in a 1:1 manner to either:

- **iovera[°] Treatment:** Subject undergoes treatment with the study device using study supplied Smart Tip.
- **Standard of Care Treatment:** Subject does not undergo iovera[°] Treatment

The Investigator or designee will record the randomization assignment in the source documentation and CRF. Any Investigator who is discovered to tamper with randomization will be immediately terminated from the study.

9.5 iovera[°] Treatment/Visit 2 (5 Days +- 2 days prior to TKA)

Medical history will be reviewed as well as concomitant medications and procedures. Blood pressure and heart rate will be assessed. The Investigator, or designee, will reconfirm all eligibility criteria are met.

The iovera[°] device will be prepared by the trained Investigator (or Sponsor designee) according to the **User Guide**. If at any time the device does not perform as expected the Investigator (or designee) will follow procedures as outlined in the **User Guide**.

Prior to the initiation of the iovera[°] treatment, the Investigator, or designee, will mark the treatment lines on the knee to be treated as shown in Figure 2 located in section 8.2.

Then the skin along the treatment lines will be cleansed with alcohol. Lidocaine, no epinephrine, will be injected along the treatment lines superficially in order to achieve cutaneous anesthesia and to the bottom of the subcutaneous layer, atop the fascia, to temporarily block conduction of the infrapatellar branch of the saphenous nerve and the anterior femoral cutaneous nerve.

Once localized anesthesia of the treatment lines and the nerves is achieved, the Investigator, or designee, will complete the iovera[°] treatment along the treatment lines. Regardless of the length of treatment lines (width of patella or from lower pole of the patella down to tibial tubercle), adjacent insertions are placed along the treatment lines until the entire line has been treated so all Subjects receive the same treatment. Treatment is not to be modified or influenced by any Subject response to changes in knee pain. Representatives of Myoscience, Inc. may be present during the treatment. Photos of the treatment area may be taken.

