9.6 Visit 3 / Total Knee Arthroplasty (Day 0)

The Investigator or Designee will confirm their ability to safely perform TKA within the following protocol requirements. All surgical and in-patient data, safety information including adverse event assessments, will be collected retrospectively from hospitalization records:

- Pre-operative History & Physical Exam, including assessment of the target knee, must be documented in the medical record and included as study data.
- Surgery and Implant - Medial parapatellar surgical approach; cruciate-retaining or posterior-stabilized TKA; all surfaces replaced.
- Pre-emptive analgesia – medications administered prior to TKA, orally, intravenously, or otherwise, for the purpose of pain management before, during, or after surgery, are to be recorded in the medical record and included as study data.
- Procedural anesthesia – during Arthroplasty this will be limited to spinal anesthesia, the formulation, or “cocktail,” of medications used are to be recorded in the medical record and included as study data.
- Local Infiltration Analgesia – The control group (standard of care) may utilize local infiltration analgesia (including periarticular and posterior capsule infiltration). The use of periarticular local infiltration analgesia (eg. Exparel) is not permitted to be used as part of this protocol in the treatment (iovera) group. However, for the treatment group, local infiltration analgesia may be used in the posterior capsule as the iovera treatment does not affect this region of the knee. The medications used in both groups are to be recorded in the medical record and included as study data.
- Regional nerve block for post-operative analgesia – single shot Adductor Canal Block required, the formulation, or “cocktail,” of medications used are to be recorded in the medical record and included as study data.
- Post-operative analgesia will be prescribed as detailed below. All opioid or other pain medications used are to be recorded in the medical record and included as study data.
 - Oxycodone, 5mg, q4h/PRN, N=40
 - Tramadol, 50mg q6, N=40
 - Tylenol, 100mg, TID, N=40
 - Neurontin, 100mg, TID, N=40
 - Meloxicam, 15mg, OD, N=15
- Post-operative discharge criteria: Ability to tolerate fluids, ambulate with physical therapist for first ambulation, Void >200cc, Pain under control.

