10.3.2 ITT (Intent to Treat) Population

All subjects who are randomized will be included in the ITT Population. Subjects will be analyzed according to the treatment group to which they were randomized. The primary analyses of effectiveness will be conducted based on the ITT Population.

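### Protocol 9.10 allows withdrawal from the whole study with no opioid or KOOS JR. collection at or after exit, so outcomes still obtainable after TKA may be imputed (cheap improvement, low priority)

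*Protocol*

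**What the plan says.** **Withdrawal.** Protocol 9.10: "A Subject may be withdrawn from the study prior to completion for any of the following reasons". Besides withdrawn consent and loss to follow-up, it lists four reasons, if non-compliance is separated from loss to follow-up, with which it shares a bullet. They are "Adverse event preventing continued study participation", an investigator's judgement that risk exceeds benefit, medical need for something prohibited, and persistent non-compliance.

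**Data at exit.** Site staff "will complete a study exit form in the CRF for any subject who prematurely discontinues from the study", and record the adverse event if it was the cause. SAP 10.0 describes exit data as the reason off study and adverse event status. Neither schedule of assessments (Protocol Table 2, SAP Table 1) has an early-termination visit. Pill counts and KOOS JR. belong to Visits 4 to 7.

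**Timing.** The device session is set at "5 Days +- 2 days prior to TKA" (heading of Protocol 9.5). The primary endpoint runs from hospital discharge to week 6 (Protocol 10.4.1).

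**Analysis.** "All subjects who are randomized will be included in the ITT Population" (Protocol 10.3.2). SAP 8.1 imputes the primary endpoint from treatment and the pill counts at Visits 4, 5 and 6. SAP 8.2 does the same for KOOS JR. with the scores at Visits 1, 4, 5 and 6. Exit reason is in neither model. SAP 8.1 also plans a TME analysis, in ITT and per protocol, that leaves out subjects who discontinued for adverse events (Tables 6.2 and 7.2).

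**Phone collection.** At Visit 4, by telephone, "Subjects will self-report the amount of opioids used" and "Subjects will report the NRS Pain Scores, answer the KOOS Jr. questions and report any AEs if present" (Protocol 9.7).

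**The concern.** During the endpoint period no device treatment is left to stop, so leaving the study then mainly stops measurement. An exit for an adverse event or on an investigator's judgement may well be related to pain and opioid need, and staff know the arm (SAP 3.3). The imputation gives a withdrawn subject values typical of someone in the same arm with the same earlier values who stayed. If withdrawn subjects differ from that, both the primary comparison and the KOOS JR. non-inferiority comparison shift, and the planned analyses would not show it. The analysis that omits adverse event discontinuations shows how far the result depends on those subjects, but it does not recover what happened to them. Adverse event recording also ends at premature withdrawal, except for device- or procedure-related events, which are followed to resolution (Protocol 11).

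**Working it through.** **Plan's own figure.** SAP 3.4 uses a difference of 12.0 mg, SDs of 18.2 (iovera) and 26.0 (control), one-sided 0.025 and 80% power. The Satterthwaite t-test needs 56 per group, and power at the stated 57 is 80.7%, so the figure reproduces. The allowance is 120 − 114 = 6 subjects, or 3 per arm. At 60 per arm power is 82.7%. If lost subjects contributed nothing, it would be 80.7% at 57 per arm (5% lost) and 78.5% at 54 (10% lost).

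**Assumptions for the bias illustration.** The documents give no withdrawal rate by arm or reason. Assume:
- k = 1 to 3 of 60 subjects in one arm are withdrawn after TKA, with no offset in the other arm;
- each has a true TME 9.1 mg/day above the imputed value (half of 18.2);
- imputed subjects otherwise count fully, so n stays at 60 per arm;
- the period is 42 days.

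**Primary endpoint.**
- SE = √(18.2²/60 + 26.0²/60) = 4.10 mg; Satterthwaite df = 105.6; critical t = 1.983.
- Bias = k/60 × 9.1: k = 1 gives 0.15 and k = 3 gives 0.46 mg/day (0.15/12 = 1.3%; 0.455/12 = 3.8%).
- All in iovera: its mean is understated. One-sided error, from the noncentral t with parameter bias/SE, is 2.7% (k = 1) to 3.2% (k = 3) instead of 2.5%.
- All in control: the difference is understated. Power, with parameter (12 − bias)/SE, is 81.7% (k = 1) to 79.7% (k = 3) instead of 82.7%.
- Equal numbers and equal excess in both arms: zero bias.
- Exit just after Visit 5, with 28 of 42 days imputed: bias × 28/42 = 0.10 to 0.30 mg/day, error 2.6% to 3.0%.

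**How high these assumptions are.** Three subjects use one arm's whole allowance, which must also cover withdrawn consent and loss to follow-up. The discharge supply is "Oxycodone, 5mg, q4h/PRN, N=40" plus 40 tramadol 50 mg (Protocol 9.6). With the SAP Appendix 2 factors this is 40 × 5 × 1.5 + 40 × 50 × 0.1 = 500 MME. An excess of 9.1 × 42 = 382 MME is 76% of it. Without refills, the imputed value could then be at most (500 − 382)/42 = 2.8 mg/day. At full frequency, oxycodone lasts 40/6 = 6.7 days and tramadol 40/4 = 10 days, so a large excess after Visit 5 needs refills or slow use.

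**KOOS JR. AUC/time.** Place change 0 at day 0 and the visits at days 3, 14 and 42. The trapezoidal weights are:
- 72 hours: (1.5 + 5.5)/42 = 0.167
- week 2: (5.5 + 14)/42 = 0.464
- week 6: 14/42 = 0.333

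Exit between Visits 5 and 6 leaves 33% of the weight imputed; exit between Visits 4 and 5 leaves 0.464 + 0.333 = 80%. If 1 to 3 of 60 subjects are 14 points worse than imputed at each missing visit, the arm mean shifts by 1/60 × 14 × 0.333 = 0.08 to 3/60 × 14 × 0.798 = 0.56 points, or 0.6% to 4.0% of the margin of 14.

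**The case against.** The wording of 9.10 is permissive, so nobody has to be withdrawn. A reader might infer that the protocol mandates data loss or that ITT fails; the text supports neither.

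The group affected is narrow. A subject who leaves before TKA has no post-discharge TME. An adverse event may truly prevent participation, and a non-compliant subject may not supply data anyway. What remains is mainly adverse event and investigator-judgement exits after surgery, and nothing in the documents shows that such a subject will also be reachable and willing.

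A reader might also infer a bias towards iovera, because periarticular infiltration is barred in that arm only (Protocol 9.6). That is the only prohibited item I found, and it is given at surgery, before the endpoint period. Nothing is listed as prohibited after discharge, and SAP Table 16 already has an analgesia deviation row. How often it would lead to an exit is unknown, so no direction follows.

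Phone report has its own weakness. A Visit 4 report can be checked against the Visit 5 count, whereas a last report by phone cannot be checked and comes from an unblinded subject, for an endpoint meant to be verified by pill count.

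The CRF pages are not available and may collect more than SAP 10.0 summarises. The SAP also appears to have been written with data in hand: 8.2 reports many missing responses on one item, and 8.4 calls some tests post hoc.

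These points limit the size, the remedy and its timing. They do not change the fact that 9.10 ends outcome collection for subjects whose outcomes might still be obtained.

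**Conclusion.** The point holds as a low-priority, cheap improvement. As written, 9.10 can replace observable primary and key secondary outcomes with values imputed under missing at random, in an unblinded trial with no device treatment left to stop. The likely effect is small and its direction cannot be derived from the documents. The upper illustration (0.46 mg/day, error 3.2% or power 79.7%; 0.56 KOOS JR. points) requires every avoidable exit to fall in one arm with the same large excess, and balanced exits give none. These figures show scale and are not estimates.

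**What to change.** Amend Protocol 9.10 so that all the listed reasons remain, as grounds for stopping study procedures or recording a deviation. A subject who has had TKA and has not withdrawn consent continues, if willing, with opioid accountability, KOOS JR., NRS and adverse event collection through Visit 6. A subject who leaves is asked for a final pill count and KOOS JR. at exit and may decline. Use a bottle count where possible and a phone report, as at Visit 4, only as a fallback. Record the source of each opioid figure, and show the primary result with and without phone-only values.

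The cost is a short amendment with IRB approval, re-consent of enrolled subjects if the IRB requires a changed form (Protocol 14.4), one CRF field, a few calls and one extra display of the primary result. No extra patients or procedures are needed. The downside is some unverified, unblinded self-report. The change helps only subjects still in follow-up when it takes effect.
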